8.	Human subject issues.....	45
8.1.	Overview.....	45
8.2.	Institutional Review Board approval.....	45
8.3.	Informed consent.....	45
8.4.	Patient confidentiality.....	45
9.	References.....	46

TONIC Trial Protocol

10. Appendices.	50
10.1. Participating centers.. . . .	51
10.2. Committees.	52
10.3. Data collection schedule.	53
10.4. Whole blood draw schedule.. . . .	54
10.5. Glossary.	55
10.6. Document history.. . . .	56

TONIC Trial Protocol

Design synopsis

Title

- Treatment of Nonalcoholic Fatty Liver Disease in Children (TONIC)

Sponsor

- NIDDK and NICHD

Objective

- To determine whether 96 weeks of treatment with either metformin or vitamin E leads to sustained reduction in serum ALT in nondiabetic children with NAFLD compared to treatment with placebo

Type of study

- Phase III randomized clinical trial
- Multicenter, masked, placebo-controlled

Treatment groups

- Group 1: Metformin, 500 mg PO b.i.d. and vitamin E-placebo b.i.d.
- Group 2: Vitamin E, 400 IU natural form PO b.i.d. and metformin-placebo b.i.d.
- Group 3: Metformin-placebo b.i.d. and vitamin E-placebo b.i.d.

Population

- Children with NAFLD aged 8-17 years at first screening visit

Study duration – per patient

- Up to 16 weeks (112 days) of screening prior to randomization, including at least 3 months of drug washout for those using antiNAFLD or antidiabetic medications prior to randomization
- 96-week treatment
- 24-week post-treatment follow-up

Study duration – per calendar time

- Recruitment phase: August 2005 - September 30, 2007
- Follow-up phase: August 2005 - October 2009

TONIC Trial Protocol

Design synopsis

Sample size justification

- Total of 180 patients in 3 groups of equal size (60 per group)
- Primary comparisons
 - Metformin vs placebo
 - Vitamin E vs placebo
- Error protection
 - Type I = 0.025 (0.05, Bonferroni protected)
 - Type II = 0.10 (90% power)
- Effect size for sustained reduction in ALT after 96 weeks of treatment
 - Expected percent with sustained reduction in the placebo group: 20%
 - Expected percent with sustained reduction in the metformin or vitamin E groups: 50%
- Statistical test and sample size software
 - Chi-squared test for two proportions
 - Dupont and Plummer PS software
- Source of data for response rates
 - Open-label pilot studies of metformin and vitamin E at the UCSD NASH CRN clinic
 - Consensus of NASH CRN clinicians regarding expected response in the placebo group

Number of clinical centers

- 8

Inclusion criteria

- Age 8 through 17 at first screening visit
- Histologic evidence of NAFLD – biopsy cannot be older than 6 months (183 days) as of randomization
- ALT level > 60 U/L on two separate occasions at least 30 days apart but no more than 12 months (365 days) apart. One of these measures must be obtained at the TONIC clinical center during screening for TONIC. The other measure may be historic (i.e., obtained prior to initiation of screening in TONIC)
- Consent
- Randomized within 16 weeks (112 days) of starting screening

Exclusion criteria

- History of significant alcohol intake (AUDIT questionnaire) or inability to quantify alcohol consumption
- Diabetes mellitus
 - Fasting serum glucose of 126 mg/dL or greater
 OR
 - 2-hour serum glucose of 200 mg/dL or greater (from oral glucose tolerance test, OGTT)

TONIC Trial Protocol

Design synopsis

OR

- History of diabetes mellitus
- ALT > 400 U/L on measurement closest in time to randomization
- Clinical or histologic evidence of cirrhosis
- Evidence of other chronic liver disease
 - Alpha-1 antitrypsin deficiency
 - Bile duct anomalies
 - Hemochromatosis
 - Hepatitis - autoimmune or viral
 - Wilson disease
- Serum creatinine of 1.5 mg/dL or greater for males and 1.4 mg/dL or greater for females
- Use of drugs historically associated with NAFLD (systemic glucocorticoids, tetracyclines, anabolic steroids, valproic acid, salicylates, tamoxifen, other known hepatotoxins) for more than 2 weeks in the 2 years prior to screening
- Use of antidiabetic drugs (insulin, biguanides, glucosidase inhibitors, sulfonylureas, meglitinides, metformin, thiazolidinediones) in the 3 months prior to randomization
- Use of antiNAFLD drugs (metformin, vitamin E, thiazolidinediones, UDCA, SAM-e, betaine, milk thistle, probiotics) in the 3 months prior to randomization
- Use of any over-the-counter or herbal remedy for hyperlipidemia in the 3 months prior to randomization
- History of metabolic acidosis
- History of renal dysfunction
- History of coagulopathy
- History of bariatric or hepatobiliary surgery
- History of total parenteral nutrition during the past 3 years prior to screening
- Inability to swallow study medication
- Vitamin E supplementation of greater than 100 I/U per day
- Disease considered by study physician to be significant
- Females of childbearing potential: positive pregnancy test during screening or at randomization or unwillingness to use an effective form of birth control during the trial
- Females of childbearing potential: breast feeding
- Any other condition, which in the opinion of the investigator would impede compliance or hinder completion of study

Outcome measures

- Primary: Sustained reduction in ALT to either 50% of baseline value or ≤ 40 U/L
- Secondary:
 - Sustained reduction in serum AST
 - Sustained reduction in serum GGT

TONIC Trial Protocol

Design synopsis

- Change in histologic feature scores determined by standardized scoring of liver biopsies at baseline and after 96 weeks of treatment
- Change in liver fibrosis, inflammation, or steatosis
- Change in body mass index
- Change in insulin resistance indices
- Change in serum vitamin E levels
- Change in serum cytokine and fibrosis marker levels
- Change in serum lipid profile
- Change in QOL scores

Randomization

- Centrally administered randomization stratified by clinical center and blocked by calendar time

Visit schedule

- Baseline/screening: at least 1 visit separated by at least 1 calendar day from randomization; screening period can last no more than 16 weeks (112 days)
- Randomization (final pre-treatment interview, dispensing of study drugs)
- Follow-up visits
 - 4 weeks after randomization
 - 12 weeks after randomization and every 12 weeks thereafter up to 96 weeks
 - 120 weeks after randomization (24 weeks after treatment ends)
- Liver biopsy at 96 week visit

Statistical analysis

- All analyses will be on an “intention-to-treat” basis

Safety monitoring

- NIDDK appointed Data and Safety Monitoring Board will monitor the data for safety and efficacy for outcomes such as metabolic acidosis, hepatotoxicity, hypoglycemia, pregnancy, new onset diabetes, and any other outcomes or events identified as safety-related
-

TONIC Trial Protocol

1. Objectives

Insulin resistance and oxidative stress (resulting in lipid peroxidation) are considered to be the two most important mechanisms in the pathogenesis of NAFLD. We hypothesize that metformin and vitamin E will lead to sustained reduction in serum ALT with biopsy proven NAFLD through changes in insulin resistance or oxidative stress.

The principal objective of this randomized, multicenter, double-masked, placebo-controlled trial is to evaluate whether 96 weeks of treatment with either metformin or vitamin E leads to sustained reduction in serum ALT in nondiabetic children with NAFLD compared to treatment with placebo.

Other objectives include:

- To evaluate changes in serum AST and GGT
 - To measure change in histologic feature scores of NAFLD
 - To evaluate change in liver fibrosis, inflammation, or steatosis
 - To evaluate change in insulin resistance indices
 - To evaluate change in serum vitamin E levels
 - To evaluate change in serum cytokine and fibrosis marker levels
 - To evaluate change in serum lipid profile
 - To evaluate changes in anthropometric measurements (weight, BMI, waist to hip ratio, waist circumference, triceps skin fold thickness, total body fat, and distribution of fat)
 - To measure change in quality of life scores
 - To assess the role of diet and activity in the development and treatment of NAFLD
 - To elucidate the natural history regarding clinical course and histology in untreated pediatric NAFLD (placebo plus diet and exercise advice)
 - To obtain serum, liver, and DNA specimens from biopsy-confirmed pediatric patients with NAFLD for subsequent studies on etiopathogenesis
-

TONIC Trial Protocol

2. Background and significance

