5.8. Adherence and retention

Two important goals of this protocol are to optimize adherence to the pharmacological regimen and to maximize the retention of participants in the study. Assessment of adherence to the assigned study drug will provide clinic staff a means to identify participants having problems with adherence. Adherence will be assessed by:

- Counts of pills in the patient's returned pill containers
- Conducting a brief, structured interview, the study coordinator will assist the patients to identify problems in taking the study drug and to estimate adherence to the assigned study drug since their previous visit.

TONIC Trial Protocol

These assessments will guide the consideration of strategies to improve adherence. Resources will be provided to remove barriers to participation such as child or elder care, transportation, and parking expenses. These resources can be provided as cash, transportation vouchers, or parking passes.

Certificates of appreciation may be given at enrollment and at conclusion as an incentive.

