6.1. Safety issues related to metformin

The following paragraphs discuss the important potential adverse effects of metformin and the proposed safeguards to minimize the risks involved.

- **Gastrointestinal side effects:** As many as 30% of patients receiving metformin report diarrhea, nausea, metallic taste, abdominal bloating, flatulence, or anorexia. We intend to minimize these side effects by recommending that metformin be taken with food and by gradually titrating the dose over two weeks.
- **Anemia:** About 6-9% of patients receiving metformin may develop reduced vitamin B12 levels. However, megaloblastic anemia is rare and metformin use has not been reported to cause peripheral neuropathy. Vitamin B12 levels will be measured at baseline and every 24 weeks until the end of TONIC trial. Patients with low B12 levels at baseline or those with diminishing B12 levels while on the protocol will be treated according to standard clinical practice.
- **Lactic acidosis** is a rare, but serious, metabolic complication that can occur due to metformin accumulation during treatment with metformin. The reported incidence of lactic acidosis in patients receiving metformin is very low (approximately 0.03 cases/1,000 patient years). However, when it occurs, the case fatality rate is 50%. We intend to minimize the lactic acidosis risk (a) by not enrolling patients with renal dysfunction in TONIC trial, (b) by not including patients with cirrhosis of the liver, and (c) by thoroughly educating the patients and investigators about avoiding intravenous contrast during the study period. If intravenous contrast is required either electively or emergently, patients will discontinue study drug on the day of dye administration for 3 days. The study drug will be restarted if the serum creatinine measured 48 hours after the contrast administration is less than 1.5 mg/dL for males and less than 1.4 mg/dL for females.

Patients in whom the study drug has been discontinued due to significant adverse effects will be followed according to the protocol and will be offered a liver biopsy at the conclusion of the study.

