7.1. Hypotheses

Primary hypotheses:

- In pediatric nondiabetic patients with NAFLD, improvement in insulin resistance over 96 weeks of treatment with metformin will result in sustained reduction in serum alanine aminotransferase (ALT) compared to treatment with placebo
- In pediatric nondiabetic patients with NAFLD, improvement in oxidative stress status over 96 weeks of treatment with vitamin E will result in sustained reduction in serum ALT compared to treatment with placebo

Secondary hypotheses:

- Treatment with metformin or vitamin E will result in sustained reduction in serum AST and GGT compared to treatment with placebo
- Metformin and vitamin E are equally effective in achieving histologic improvement in nondiabetic children with NAFLD
- Levels of proinflammatory cytokines and serum markers for fibrosis will decrease with treatment with metformin and with vitamin E compared to treatment with placebo
- Pediatric nondiabetic patients with NAFLD have an impaired quality of life, and these scores will improve as their serum ALT improves upon treatment with metformin or vitamin E compared to treatment with placebo

Other questions to be addressed:

- We predict that insulin resistance is common in pediatric nondiabetic patients with NAFLD and will be significantly related to waist-to-hip ratio, waist circumference, serum ALT, and hepatic histology
- We predict that degree of obesity will be significantly related to hepatic histology in pediatric nondiabetic patients with NAFLD and more severe obesity (BMI or BMI z score) will be related to greater elevations in ALT and more advanced hepatic histology

- We predict that serum markers for steatosis, inflammation, and fibrosis will be significantly related to hepatic histology in pediatric nondiabetic patients with NAFLD
- We predict that worsening hepatic histology will be significantly related to a worsening in health-related quality of life in pediatric nondiabetic patients with NAFLD and more advanced histology will have worse health-related quality of life as measured by scores on the PedsQL
- We predict that improvement in the measures of insulin resistance will be significantly related to improvements in liver histology, serum ALT, and serum markers for steatosis, inflammation, and fibrosis in pediatric nondiabetic patients with NAFLD
- We predict that therapy with vitamin E will improve insulin resistance in pediatric nondiabetic patients with NAFLD

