7.3. Statistical analysis

Primary hypotheses:

Statistical analyses for the two primary hypotheses will follow the intention-to-treat paradigm, which means that all randomized patients with baseline and 96 week serum ALT values will be analyzed in the treatment group to which they were assigned. Any randomized patient who does not have the requisite ALT values will be accounted for and compared by assigned treatment group. Patients not able to be included in the intention-to-treat analyses will be compared to those who are included with respect to demographic and other characteristics.

Since the primary outcome measure, defined in Section 7.2, is a binary indicator of sustained reduction in ALT after 96 weeks of treatment compared to baseline and since the randomization is stratified by clinic, P-values for the primary hypotheses will be derived from the Mantel-Haenszel χ^2 test for stratified 2x2 tables⁴⁴. Two P-values will be derived: one comparing proportions improved in the group assigned to metformin compared to the group assigned to placebo and another comparing the group assigned to vitamin E to the group assigned to placebo. Since two primary comparisons are planned, a P-value of 0.025 will be considered significant, applying a Bonferroni correction for multiple comparisons.

Given the randomized design and adequate size planned for the TONIC trial, it is unlikely that confounding of the treatment groups by covariates related to the change in serum ALT will occur. However, if confounding should occur, logistic regression analyses with sustained reduction in ALT as the binary response and treatment group indicators and any suspected confounders as covariates will be carried out to determine the sensitivity of the primary P-values to confounding.

Secondary hypotheses:

Statistical analyses for the first secondary hypothesis, that treatment with metformin or vitamin E will result in sustained reduction in serum AST and GGT compared to treatment with placebo, will be the same as described for primary hypotheses.

The second secondary hypothesis, that metformin and vitamin E are equally effective in achieving histologic improvement in nondiabetic children with NAFLD, involves the histologic outcome measure. Equivalence will be assessed by means of 95% confidence intervals on the difference in proportions improved.

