7.4. Missing data

The occurrence of missing data in TONIC trial is expected to be low and, when present, is expected to be equally distributed across the 3 treatment groups. We estimate that careful selection of patients during the 16 weeks screening phase and the consent process should result in no more than 10% missing data from patients who drop out before completing the 96 week treatment period. In primary, intention-to-treat analyses, patients with missing data will be considered unimproved on the primary outcome measure.

The proportions with missing data will be compared across treatment groups using χ^2 tests. If the amount of missing data exceeds 10% and the frequency of missing data differs by treatment group, then a variety of sensitivity analyses will be carried out to compare with the primary analysis using all available non-missing data: (1) compare pessimistic and optimistic imputations of the missing values, (2) correct for missing data using multiple imputation with 10 replicated samples, and (3) use mixed random effects logistic or linear regression models, depending on the type of outcome measure.

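### The hypothesis that metformin and vitamin E are equally effective on histology rests on intention-to-treat alone, which is not conservative for an equivalence claim; an on-treatment interval and a stated margin would be a cheap improvement

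*Supplement*

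**What the plan says.** The Statistical analysis entry of the design synopsis reads "All analyses will be on an “intention-to-treat” basis", with no exception. Section 7.1 lists as the second secondary hypothesis: "Metformin and vitamin E are equally effective in achieving histologic improvement in nondiabetic children with NAFLD". Section 7.3 gives the method: "Equivalence will be assessed by means of 95% confidence intervals on the difference in proportions improved". It states no margin and no decision rule, and neither 7.3 nor 7.4 plans an on-treatment or per-protocol analysis.

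For the primary hypotheses, section 7.3 describes intention-to-treat as meaning that "all randomized patients with baseline and 96 week serum ALT values will be analyzed in the treatment group to which they were assigned". Section 7.4 adds: "In primary, intention-to-treat analyses, patients with missing data will be considered unimproved on the primary outcome measure". No rule is given for a missing week-96 biopsy.

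The protocol foresees children off drug. Section 6.3 keeps those who stop after a failed reintroduction in follow-up. Section 6.1 offers a biopsy to those stopped for significant adverse effects. Sections 5.9 and 6.9 list lasting stops for major skin reactions, pregnancy and some new-onset diabetes. Adherence is recorded: section 5.8 provides for pill counts and for an interview to "estimate adherence to the assigned study drug since their previous visit".

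**The concern.** In the comparisons with placebo, children who stop drug but stay in their assigned arm dilute the effect and make a false positive less likely. In an equivalence comparison the same dilution brings the arms closer and makes the favourable conclusion easier to reach. An intention-to-treat interval alone therefore cannot separate two drugs with similar effects from two drugs that look similar because children stopped taking them.

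At stake is one secondary conclusion: that two drugs with different mechanisms improve histology equally well. The two primary ALT comparisons are not touched.

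**Working it through.** **The plan's own figure.** Section 7.5 uses rates of 0.20 and 0.50 (mean 0.35), two-sided alpha 0.025 and 90% power:

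n = [2.2414·√(2·0.35·0.65) + 1.2816·√(0.16 + 0.25)]² / 0.30² = [1.5119 + 0.8206]² / 0.09 = 60.45.

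This agrees with the stated 60 per group. That size was set for the ALT comparisons with placebo; nothing was computed for equivalence.

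**Inputs for the check.** From the plan: 60 per arm and a 95% interval on the difference in proportions. Assumed, because the plan gives no values: a margin M of 20, 25 or 30 points; on-drug histologic improvement centred on 50%; 30% improvement off drug in either arm; and off-drug shares d of 0, 10 and 20%.

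**Dilution.** Observed rate = (1 − d)·p_on + d·0.30. With the same d in both arms, observed difference = (1 − d) × on-drug difference. Example, M = 25 points and d = 20%: 0.8·0.625 + 0.2·0.30 = 0.56 and 0.8·0.375 + 0.2·0.30 = 0.36. The difference falls from 25 to 20 points.

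**False equivalence.** The on-drug difference is set equal to M. The table gives the exact binomial probability that the Wald 95% interval lies wholly within ±M.

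| Off drug, each arm | M = 20 | M = 25 | M = 30 |
|---|---|---|---|
| 0% | 2.0% | 2.5% | 2.4% |
| 10% | 3.1% | 4.6% | 5.1% |
| 20% | 4.7% | 8.0% | 9.7% |

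Other assumptions (better arm at 50%, 20% improvement off drug) give a similar picture: 1.9, 2.3 and 2.3% with full adherence; 3.1, 4.4 and 5.2% with 10% off drug; 5.1, 8.1 and 10.5% with 20% off drug.

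**Unequal stopping.** Take 20% off metformin and 5% off vitamin E.
- Metformin truly better: 6.2, 10.1 and 11.3%.
- Vitamin E truly better: 1.7, 2.6 and 2.9%. The observed differences are 20.5, 24.9 and 29.3 points, so there is hardly any shrinkage.
- Drugs truly equal at 50%: (0.8·0.5 + 0.2·0.3) − (0.95·0.5 + 0.05·0.3) = 0.46 − 0.49 = −3 points, a spurious difference.

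**Missing biopsies.** Scoring a share m as unimproved multiplies both rates, and so the difference, by (1 − m). With 20% off drug and m = 10%, false equivalence would be 6.3, 11.6 and 15.1%. If biopsies missing at random are left out, the difference does not shrink and the interval widens.

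**What 60 per arm can show.** At rates of 50% the half-width is 1.96·√(2·0.25/60) = 17.9 points. If the drugs are truly equal, the interval falls within ±20, ±25 and ±30 points 22, 59 and 83% of the time. With 30% off drug, 42 per arm remain on treatment. The half-width is then 1.96·√(2·0.25/42) = 21.4 points, and a 20-point margin is essentially never met.

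**The case against.** The strongest reply is that without a margin the plan has no formal finding of equivalence, so no nominal error rate can be exceeded. That stands. The percentages above describe what would happen once a margin was chosen, and the absent margin is the larger gap.

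The off-drug shares are also assumptions. A reader might take section 6.1 ("As many as 30% of patients receiving metformin report diarrhea, nausea, metallic taste, abdominal bloating, flatulence, or anorexia") as a stop rate. It counts symptom reports, before the mitigation by food and titration, and section 3.3.1 reports no gastrointestinal drop-outs among ten children on the same dose. Likewise, the 13 new-onset diabetes cases forecast in sections 6.2 and 6.3 are for the placebo and vitamin E arms. They are not all stops: section 6.9 ends treatment only on a further glucose criterion.

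A reader might further infer that missing biopsies necessarily pull the arms together. The documents do not support this: section 7.4 says that "patients with missing data will be considered unimproved on the primary outcome measure", which concerns ALT, and no histologic rule is given. Nor is the bias always towards equivalence, as the unequal-stopping figures show.

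Finally, an on-treatment set is selected after randomization and can itself be biased, and section 7.4's neighbour, the secondary-analysis text in 7.3, already asks for cautious reading of significant secondary findings. The first is a reason to report the on-treatment interval beside the intention-to-treat one, not in its place. The second does not tell a reader how much dilution a finding of no difference contains.

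**Conclusion.** The point holds as a modest, inexpensive improvement. The plan puts an equivalence hypothesis on intention-to-treat alone and plans no on-treatment companion. Given similar off-drug shares and a similar off-drug response in both arms, false equivalence rises from about 2 to 2.5% to 3.1–5.1% with 10% off drug and 4.7–9.7% with 20% off drug, at assumed margins of 20 to 30 points. The margins, histologic rates and off-drug shares are assumptions. With unequal stopping the error can stay near 1.7–2.9%, or truly equal arms can be pushed apart. The documents do not show that equivalence will be falsely found, that missing biopsies will add to the shrinkage, or that intention-to-treat is wrong for the other metformin–vitamin E comparisons.

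**What to change.** Keep intention-to-treat for all comparisons and leave the synopsis sentence as it is. In section 7.3, for the metformin–vitamin E histologic equivalence hypothesis only:

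- state an equivalence margin with its justification;
- state that a missing week-96 biopsy is not scored as unimproved;
- add an on-treatment interval, in children on assigned drug at week 96 with pill-count adherence above a pre-set cut-off, beside the intention-to-treat interval;
- call the drugs equally effective only if the intention-to-treat interval lies within the margin and the on-treatment result is consistent with it.

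The cost is a few sentences and one analysis of data already collected. The on-treatment set is smaller, has a wider interval and is not protected by randomization. Equivalence will therefore be harder to show, which is why the on-treatment result is asked to be consistent and not to meet the margin on its own.
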